4. STUDY DESIGN

4.1. Type and design of the study Pilot study of phase I, open, two-branch, **multicentre** clinical trial for the study of the efficacy of passive immunization through repeated infusion of plasma from people exvalescing from infection with COVID-19 and/or with a negative viremia result for COVID-19, together with the standard treatment that is currently being scheduled, compared to the exclusive application of standard treatment in currently hospitalized COVID-19 patients. **The study will be carried out and coordinated by HUSLL, which may be joined by all health centres interested in participating in the study that meet the requirements to be able to develop it and commit to the conditions of the same. In each centre, the study subjects will be selected among those admitted to both the COVID-19 plant and the ICU (or their counterpart places in each centre).** Below is an outline of the study design:

[figure not shown]

Fig 1. Outline of the design of the study protocol to be carried out.

IMPORTANT NOTE: the scheme refers to the coordinating centre (HUSLL), but the same conditions are extended to all those centres participating in the multicentre study.

The assignment to the control and intervention groups, both in the plant and in the ICU, will be done by means of simple random assignment, using equiprobability calculations through a computer system, in order to guarantee that all subjects have the same probability of belonging to the two groups. The system will be the same in all participating centres. This system will be carried out whenever a plasma stock is available. In the event that the stock runs out, the recruited patients will be part of the control group.

The characteristics of the experimental groups are detailed below:

-For intervention group: usual standard treatment (according to clinical guideline for COVID-19), plus two infusions followed by a volume equal to 300 ml of plasma from patients convalescing from COVID-19 and with negative viremia in the COVID-19 detection test and therefore discharged and / or cured. The infusions will be given on days 1 and 2 of study, after the positive result for COVID-19 of the recipient patient, who will be treated.

-For control group: usual standard treatment, according to clinical guideline for COVID-19. This is based on any drug used in clinical practice accepted to date, from retroviral (lopinavir/ritonavir;

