darunavir/cobicistat; remdesivir), interferon- α/β , anti-IL-6 monoclonal antibody (Tocilizumab) or oxygen therapy among others. The ratio controls: treated will be 1:2 in favour of the treatment. As treatments have been changing throughout the pandemic, when performing the final analysis, a stratified analysis will be made by type of treatment. That is, infected patients who have been treated with the same drugs will be compared.

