4.2.4. Research treatment

1. Description of the processing

Plasma of convalescent patients with antibodies against Coronavirus SARS-CoV-2 compatible with receptor. **This plasma will reinforce the standard treatment that will be prescribed in these patients, following the guide of "Clinical management of COVID-19 patients", where the usual medications in these patients and their management are detailed.**

2. Labelling and storage of research processing

The plasma will be labelled and stored as set forth in the apheresis section of the receiver.

3. Administration of study treatment

600 ml of plasma from ex-convalescent patients' compatible ABO group shall be administered peripherally or centrally intravenously every 24 hours on days 1 and 2 from treatment assignment, divided into two doses of 300 ml each. **The 600 ml of plasma will ideally come from a single donor patient, failing that plasma from different donors may be administered if they are from the same compatible ABO group, recording the final titration of the two doses administered.**

5. Accounting of the study treatment

The principal investigator of the study will be responsible for the registration of the transfused plasma units using the accounting form. Patient code, identification code of the administered plasma unit, expiration date and date of administration must be recorded. This form must be kept together with the documentation of the study in case of audit or inspection.

6. Description of control treatment

The control treatment will consist of what is indicated in the COVID-19 management protocols according to usual clinical practice and in accordance with the clinical management protocol of the patient hospitalized for COVID-19. The full duration of the treatment will be determined by what is specified in the protocols. All medication will be provided by the pharmacy service of the Son Llàtzer University Hospital (or where appropriate the pharmacy services corresponding to each centre participating in the study), following usual clinical practice.

7. Criteria for discontinuation of study treatment

The following situations will lead to permanent discontinuation of study treatment:

- Exitus.
- Life-threatening toxicity to the patient, including infusion-related reactions.

8. Concomitant medication

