Since from the beginning of the pandemic to the present day no effective treatment against SARS-CoV-2 infection has been found; whereas it has also been shown that the disease has a high probability of progressing rapidly into more severe forms, causing death even in vulnerable groups; whereas the forecast for late summer-start autumn 2020 is being met; whereas there are no prevalence/incidence numbers or any other type of definitive numerical data that allows canonical sample size calculations to be made; whereas the few studies that have been published on the treatment of hyperimmune plasma infection have shown a positive trend towards decreasing symptoms and severity; and that finally we continue to find ourselves in a health emergency situation; so for all these reasons this study is transformed into a multicentre study, at the request of the participating centres. Therefore, it is required, in order to estimate with maximum efficiency, the effect of this therapy, the maximum number of donors and the maximum number of possible recipients. Each case is explained below:

-For donors: it is required to collect the plasma sample from the maximum number of people who meet the requirements to be donors. This aims to create an anti-SARS-CoV-2 hyperimmune plasma bank, so that not only for this study, but for serious situations in which all the possibilities available so far have been exhausted, this therapy can be used as an alternative. The difficulty of finding suitable donors, who not only meet the requirements to be donors, but also have a sufficient antibody titration, forces us to make accurate donor lists in order to have this type of sample in sufficient quantity. Being a multicentre study, more doses of plasma will be needed to be able to supply all the centres. Considering that the ratio is 1 donor or 1 donation for each recipient.

-For recipients: as it is unknown how many patients can progress in the coming weeks/months with COVID-19, it is required to propose participation in the study to all patients who are diagnosed with COVID-19 and admitted to the plant or ICU for COVID-19 of all participating centres. In this way, the maximum number of patients can be collected, in order to cover a sufficient sample size in the two branches of comparison of the study (control and treatment). As patients are admitted, they will be proposed to participate by explanation and with the HIP, and if they sign the IC, they will become part of it.

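### Section 4.1 is inconsistent on allocation: equiprobable assignment naturally means 1:1, the stated ratio is 1:2, and the stock-out rule cannot reconcile them

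*Combined protocol and SAP*

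**What the plan says.** All the statements on allocation are in section 4.1 of the current text.

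- **Mechanism.** Patients in both plant and ICU are allocated by simple randomisation, which the section describes as "using equiprobability calculations through a computer system, in order to guarantee that all subjects have the same probability of belonging to the two groups". One arrangement serves every site: "The system will be the same in all participating centres".
- **Stock-out rule.** Random assignment operates only while plasma is available. Otherwise, "In the event that the stock runs out, the recruited patients will be part of the control group".
- **Ratio.** After describing the control treatment, the section adds: "The ratio controls: treated will be 1:2 in favour of the treatment".

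Two further places bear on plasma supply. Section 4.2.10 says "Considering that the ratio is 1 donor or 1 donation for each recipient". Section 4.2.4, item 3, says "The 600 ml of plasma will ideally come from a single donor patient" and allows several donors if that fails.

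No other visible text gives an assignment probability, a weighting or a block scheme. Annex IX says only that the study branch is returned in reply to the inclusion email, and section 5 (statistics) does not mention allocation.

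**The concern.** A single computer system needs a single assignment probability, and section 4.1 supports two. Someone setting up the system, or auditing it later, cannot tell which setting complies with the protocol.

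The choice has two practical consequences. It sets how fast a scarce product is used. It also affects how soon the stock-out rule takes over, after which every new recruit becomes a control without randomisation. Section 4.1 does not say whether those recruits count towards the 1:2. The ratio question and the make-up of the control group are therefore connected.

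**Working it through.** **Inputs.** From section 4.1: equiprobable simple assignment, a 1:2 control-to-treated ratio, and the stock-out rule. The protocol gives no total sample size and no expected stock-out fraction, so the values of N, s and D below are assumptions.

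**1. The plan's own ratio.** A 1:2 ratio means a plasma share of 2/(1+2) = 66.7%, which needs probability p = 2/3. Equiprobable assignment to two groups means p = 1/2, a share of 50% and an expected 1:1. The stated ratio is not reproduced by the stated mechanism on its natural reading.

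**2. Could chance produce it?** Under p = 1/2, the exact binomial probability that at least two thirds of patients receive plasma is 4.9% at an assumed N = 30 and 0.67% at N = 60.

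**3. Could centres or wards explain it?** No. The same system applies at all centres, and the assignment method covers plant and ICU alike.

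**4. Could the stock-out rule explain it?** Let s be the fraction of all recruits who enter during a stock-out. The overall expected plasma share is (1 − s) × p, which is below p whenever s is above zero. Stock-out recruits as a share of all controls are s / (1 − (1 − s)p).

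| Assumed s | Plasma share, p = 1/2 | Plasma share, p = 2/3 | Stock-out share of controls, p = 1/2 | Stock-out share of controls, p = 2/3 |
|---|---|---|---|---|
| 10% | 0.9 × 1/2 = 45% | 0.9 × 2/3 = 60% | 0.10/0.55 = 18% | 0.10/0.40 = 25% |
| 20% | 0.8 × 1/2 = 40% | 0.8 × 2/3 = 53% | 0.20/0.60 = 33% | 0.20/0.467 = 43% |
| 50% | 0.5 × 1/2 = 25% | 0.5 × 2/3 = 33% | 0.50/0.75 = 67% | 0.50/0.667 = 75% |

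The rule moves the share away from 67% under either probability. To reach 1:2 overall, the in-stock probability would have to be (2/3)/(1 − s), which is 0.74 at s = 10% and 0.83 at s = 20%. It reaches 1 at s = 1/3, so beyond that point an overall 1:2 is unattainable.

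**5. Plasma use.** For the same number of in-stock patients, relative use is (2/3)/(1/2) = 1.33, or one third more. A fixed stock that treats D patients lasts on average for D/p assignments: 2.0 × D under 1/2 and 1.5 × D under 2/3, which is 25% fewer. With an assumed D = 20, that is 40 against 30 patients. The relative figures carry the argument; the counts only illustrate it.

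**The case against.** **A compatible reading exists.** The stated aim, "in order to guarantee that all subjects have the same probability of belonging to the two groups", could mean that every subject has the same chance as every other subject, for example 2/3 each. That would fit 1:2. It is the weaker reading, because equiprobability and the reference to the two groups point to 1/2 and no weighting is given. It also fits 1:2 only among patients assigned in stock. Figures 1 and 2 and the recipient information and consent annexes are not shown and might state the chance of assignment. For that reason the point is that the visible text is inconsistent and unsettled; it does not show that 1:2 was never intended.

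**A reader might infer that planned supply is wrong, or that fixed donation numbers follow.** The documents do not support that. Section 4.2.10 sets no donation target; it seeks as many donors as possible. Its recipients may be all enrolled patients, since section 4.2.1 uses the word for the whole sample. On that usage, one donation per recipient would be enough under either probability. Absolute counts are also fragile:

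- Section 4.2.4 allows plasma from several donors.
- Annex VIII, section 3.4, caps extraction at 13% of the donor's volume (455 ml at 50 kg, 637 ml at 70 kg).
- Sections 4.2.4 and 4.2.8 require ABO compatibility.
- Section 4.2.6 gives the coordinating hospital priority for its own product.

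The one-third relative difference in use survives these objections.

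**The non-random controls are a separate problem.** They would arise under any ratio, so this is partly right. The two still belong together: a ratio cannot be stated properly without saying which patients it covers, and a higher probability brings the stock-out rule into play sooner.

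**Conclusion.** The inconsistency stands. Section 4.1 gives 50% plasma on the natural reading of its mechanism and 67% by its stated ratio. Nothing visible reconciles them, and the stock-out rule widens the gap. Under 2/3, in-stock patients use one third more plasma than under 1/2. At any given stock-out fraction, a larger part of the control group is then non-randomised (25% against 18% at an assumed 10%). All figures that involve stock-outs rest on assumed fractions.

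A reader might infer that the trial is invalid or underpowered because of this. The documents do not support either. Each ratio, applied consistently, gives a valid randomised comparison among patients randomised in stock. The protocol states no sample size, effect size or power that the ratio could change. The point should be fixed because a basic design parameter is stated in two ways and the correction is cheap.

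**What to change.** 1. **State one ratio and the matching probability in section 4.1, and say that it applies to patients assigned while plasma is in stock.**
   - For 1:1, keep the equiprobable mechanism and delete the 1:2 sentence.
   - For 1:2, replace the equiprobability clause with: *using a computer system that assigns each subject to plasma with probability 2/3 and to control with probability 1/3*. Keep simple random assignment in plant and ICU. Keeping the computer system in the wording also preserves what the next sentence, on the same system at all centres, refers to.
2. **Record stock status (yes/no) at assignment.** Base the main plasma-versus-control comparison on patients randomised while plasma was in stock. Report stock-out recruits separately as non-randomised controls, with a sensitivity analysis that includes them.

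**Cost.** A few sentences, one system setting and one data field. The main comparison also loses the stock-out controls, in the proportions shown in the last two columns of the table above. They remain in the study and in the sensitivity analysis. Section 4.3.2 already extends the study period to recruit enough patients, so continued recruitment can offset the loss.

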3. HYPOTHESIS AND OBJECTIVES

3.1. Hypothesis:

Plasma from people who have been infected and have overcome the COVID-19 disease is expected to have sufficient and compatible levels of antibodies (anti-COVID-19) to neutralize the viral load that a person infected and still convalescing with COVID-19 may present. Therefore, it is expected that the efficacy of the reinforcement of standard therapy with repeated transfusion of immune plasma from COVID-19 convalescents vs standard therapy alone in hospitalized COVID-19 patients will be more effective at the therapeutic level and may be a possible palliative until the discovery of a vaccine. Mitigating the inflammatory phase of the disease and therefore reducing the risk of ARDS.

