3.2. Objectives

3.2.1. Main objective:

The objective of the study is to determine the efficacy of reinforcing standard treatment with repeated infusions of plasma from people ex-convalescent of COVID-19 disease (already discharged and/or with negative COVID-19 test results), transfused to COVID-19 patients still hospitalized, both COVID-19 plant and HUSLL ICU ([and collaborating centres participating in the multicentre study](#)). Comparing it with the results obtained with the exclusive use of standard treatment, which is being used in patients infected with COVID-19. Therefore, to assess the immunological efficacy of the reinforcement of standard treatment vs standard therapy without reinforcement.

3.2.2 Secondary objectives:

Secondary objectives are related to evaluating not only efficacy at the clinical level, but also tolerance, safety and immunological aspects. Below is a list of the main secondary objectives:

- To assess the serological response to Coronavirus SARS-CoV-2 in patients with plasma transfusion and compare it with patients who have received treatment standard.
- Analyse the influence of the number of antibodies of the donor on the clinical evolution of the recipient.

-Analyse the efficacy of the experimental treatment that will reinforce the standard treatment, comparing it with the exclusive standard treatment at the level of the main clinical parameters during and after the treatment.

-To assess the safety of experimental reinforced treatment, comparing it with standard treatment during and after treatment.

-To assess the tolerance of experimental reinforced treatment, comparing it with standard treatment during and after treatment.

-Evaluate the feasibility of the experimental reinforced treatment.

-To assess the virological response of patients with plasma transfusion versus patients with standard treatments.

-Find if there is a certain patient profile where this therapy is most effective, either by age group, blood group, sex, or presence/absence of other pathologies.

-On the contrary, determine if there is a certain profile of patients (as in the previous case) in which the treatment is less effective.

-To know retrospectively the parameters of antigenemia and viral load of convalescent patients infected by COVID-19.

-Find possible weak points of experimental therapy that need to be studied to be improved in future studies.

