Any concomitant medication is allowed for the treatment of concomitant pathologies presented by the patient as well as the symptoms associated with COVID-19, including standard anticoagulant treatment that is prescribed under normal conditions (if applicable).

9. Prohibited medication

There is no contraindicated medication in the study treatment.

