5. DATA ANALYSIS: STATISTICS

A descriptive analysis of all variables will be performed. With the categorical variables, the global percentages and frequencies will be estimated. Normality tests and graphs will be used to determine if the quantitative variables follow a normal distribution. Normal distribution variables shall be expressed as mean \pm standard deviation and those without normal distribution shall be expressed as median and interquartile range. To describe the significance and associations between variables after the intervention, parametric and non-parametric tests will be used as appropriate (the student's t test of paired samples or the Wilcoxon test for quantitative variables and the ANOVA test for paired samples or Friedman test for qualitative variables). The correlations will be examined by the correlation of Spearman or Pearson ranges and a multivariate analysis will be performed to assess the effect of other factors such as the confusion/interaction effect, as well as to assess the possible construction of predictive models. A p-value $< 0,05$ shall be considered an indicator of a significant difference. SPSS v.23 software will be used for data analysis.

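### The planned strata by drugs received are not limited to treatment in use before assignment, so the stratified comparison can condition on what happens after it

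*Combined protocol and SAP*

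**What the plan says.** Section 4.1 lists the standard treatments that both arms may receive. The list is open-ended and includes antivirals, interferon, tocilizumab and oxygen therapy. The section then says: "As treatments have been changing throughout the pandemic, when performing the final analysis, a stratified analysis will be made by type of treatment". It explains: "That is, infected patients who have been treated with the same drugs will be compared". It does not say as of when the drugs are counted.

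Other places bear on this:

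- Section 4.1 describes an open trial, and Annex IX has the treating physician told the patient's arm.
- Section 4.2.4, item 8: "Any concomitant medication is allowed for the treatment of concomitant pathologies presented by the patient as well as the symptoms associated with COVID-19".
- Section 3.1 gives an expected action of plasma: "Mitigating the inflammatory phase of the disease and therefore reducing the risk of ARDS".
- Section 3.2.1 states the main comparison: "Comparing it with the results obtained with the exclusive use of standard treatment".
- Section 5 does not mention the drug strata. It adds that "a multivariate analysis will be performed to assess the effect of other factors such as the confusion/interaction effect", without restricting those factors to baseline.
- Section 4.3.1 and its Table 3 review concomitant medication at screening and on days 1, 2, 3, 7, 14 and 21. Table 1 in section 4.3.3 records whether a drug was given and its name, but no start date.
- The WHO Progression Scale in Table 1 uses oxygen and ventilation to define several of its levels.

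**The concern.** Stratifying on a characteristic fixed before assignment leaves the arms comparable within each stratum. Stratifying on something that happens afterwards need not, because the arm may influence who enters which stratum.

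The documents supply a route for that influence. Physicians know the arm, may add any drug, and are treating a disease whose inflammatory phase plasma is hoped to dampen. Two things can follow:

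- If plasma prevents some deterioration, part of its benefit shows up as fewer patients needing added treatment. Comparing only patients with the same drugs removes that part.
- If plasma does nothing but prescribing differs by arm, patients with the same drugs differ in prognosis between arms, and a difference appears that is not real.

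Oxygen sharpens the problem. If it counts as a treatment for the strata, the analysis conditions on something that also defines levels of an outcome scale.

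**Working it through.** **No plan figure to reproduce.** Section 4.2.10 gives no sample size, effect size or event rate. Every rate below is therefore an assumption, and only mortality is modelled, not antibody titre or PCR. Negative differences favour plasma.

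**Inputs (assumed).** Deterioration: 40% on control, 20% on plasma. Mortality: 40% if deteriorated, 2% if not. A later drug is given to a share *a* of deteriorating patients and *b* of the others. Plasma acts only through deterioration.

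**Formulas.** With *d* the deterioration risk in an arm:

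- Drug share = d·a + (1−d)·b
- Mortality in drug stratum = [d·a·0.40 + (1−d)·b·0.02] / drug share
- Mortality in no-drug stratum = [d(1−a)·0.40 + (1−d)(1−b)·0.02] / (1 − drug share)
- Stratified estimate = the two stratum differences weighted by the pooled shares with and without the drug

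**Case 1: same prescribing rule in both arms, drug has no effect on death.** True difference = (0.20 − 0.40) × (0.40 − 0.02) = −0.0760.

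Worked example, a = 0.80, b = 0.05, arms of equal size:

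- Control: drug share 0.32 + 0.03 = 0.35; mortality 0.1286/0.35 = 0.3674 with the drug and 0.0434/0.65 = 0.0668 without.
- Plasma: drug share 0.16 + 0.04 = 0.20; mortality 0.0648/0.20 = 0.3240 with and 0.0312/0.80 = 0.0390 without.
- Differences −0.0434 and −0.0278; pooled drug share 0.275.
- Estimate = 0.275 × (−0.0434) + 0.725 × (−0.0278) = −0.0321, or 42% of the truth.

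| a / b | Stratified estimate (points) | Share of the true −7.6 |
|---|---|---|
| 100% / 0% | 0 | 0% |
| 80% / 5% | −3.2 | 42% |
| 60% / 5% | −4.8 | 64% |
| 40% / 5% | −6.2 | 81% |
| 40% / 20% | −7.3 | 96% |
| 20% / 10% | −7.5 | 98% |

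**Case 2: the drug cuts mortality of deteriorated patients by 25%.** The estimates are −2.9 against a true −6.0 (80%/5%), −4.5 against −6.4 (60%/5%) and −6.7 against −6.8 (40%/20%).

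**Case 3: no plasma effect, prescribing differs by arm.** Deterioration is 40% in both arms, b = 5%, and a = 80% on control but 60% on plasma. Control is as in the worked example. Plasma has drug share 0.24 + 0.03 = 0.27, with mortality 0.0966/0.27 = 0.3578 with the drug and 0.0754/0.73 = 0.1033 without. The differences are −0.0097 and +0.0365, and the pooled drug share is 0.31. Estimate = 0.31 × (−0.0097) + 0.69 × 0.0365 = +0.0222, a false harm of 2.2 points.

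**Case 4: strata nearly closed before assignment.** If only 10% of later starts leak into the strata (a and b multiplied by 0.10), the 80%/5% row of case 1 becomes −7.3 (96% of the truth) and the false effect in case 3 becomes +0.2.

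**Allocation ratio.** Section 4.1 speaks both of equal probability and of a 1:2 ratio. At 1:2 every result above moves by less than 0.1 point.

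**A different model as a check.** Take two equally common severity groups with control mortality of 10% and 40%, control use of a later drug of 20% and 70%, and Mantel-Haenszel weights. With no plasma effect, the estimate is 0 if drug use does not depend on arm. It is +1.1, +2.2 or +4.0 points as plasma-arm use falls to 15%/60%, 10%/50% or 5%/30%, and −2.0 if use rises to 30%/85%. A true −7.5 (risk ratio 0.7) shrinks to −6.6, −5.6 or −4.0 under the same three reductions. The distortion can go either way, and it is zero when later drug use does not depend on arm.

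**The case against.** The strongest reply is that the harmful reading is not the natural one. The rule follows directly on the list of standard treatments and is justified by treatments changing over the pandemic, which describes background regimen over calendar time. Section 4.2.4 says which drugs are permitted, not that they define strata. This stands as evidence of intent. It does not limit the rule, because the defining sentence is wider than its motive and no other section narrows it.

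A reader might infer that the drug-stratified comparison is the primary or only comparison of the arms. The documents do not say so: section 3.2.1 sets an overall comparison with standard treatment, and nothing states that the strata replace it. A reader might also lean on the tests named in section 5 ("the student's t test of paired samples or the Wilcoxon test for quantitative variables") to argue that no other comparison between arms exists. That goes too far. The section says tests will be chosen as appropriate, and its multivariate analysis could include arm. Those tests are a separate issue and add no weight here.

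On size, the reply is also fair. All rates are assumed, a halving of deterioration acting as the only pathway favours large distortion, and with weakly targeted prescribing 96% to 98% of the effect survives. At an assumed 100 patients per arm and the 17.2% mortality of case 3, the standard error is √(2 × 0.172 × 0.828 / 100) = 5.3 points, so a false 2.2 points is under half of one. The near-recovery in case 4 follows from its assumption of 10% leakage.

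Finally, strata closed strictly before assignment have a weakness of their own. Screening and day 1 may coincide, so standard therapy begun on or just after assignment could be classed as no drug. This stands and shapes the fix.

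**Conclusion.** The point holds as a gap in an operative rule. As worded, the stratified final analysis can condition on treatment started after assignment, and nothing elsewhere in the documents prevents it. It does not show that the investigators intend this, nor that the trial's main comparison is distorted.

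The size cannot be fixed from the documents. Under the assumed rates, the stratified estimate keeps between none and 98% of a true mortality difference, and a null effect can appear as roughly −2 to +4 points. Distortion needs later treatment to depend on arm, through plasma's own effect or through open prescribing, and to be related to prognosis. The calculation says nothing about antibody or virological outcomes. The change is worth making because it is cheap and serves the plan's stated purpose better, not because a large bias has been demonstrated.

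**What to change.** In section 4.1 and section 5:

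- Define the strata or adjustment factors by calendar period of enrolment as the main choice, since it directly addresses changing treatments and cannot be affected by arm. Add or substitute, if wanted, the standard regimen prescribed at or before assignment. Include ward or ICU.
- State that patients are compared by assigned arm, both overall and within those strata.
- Report drugs and oxygen started after assignment descriptively by arm, and label any analysis by treatment received as exploratory.
- Limit the adjustment factors of the multivariate analysis in section 5 in the same way when it is used to estimate the plasma effect.

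The cost is mostly wording. The visit-level medication reviews already separate earlier from later drugs. A start date may be needed for drugs begun on day 1 or when screening and day 1 coincide. If drug strata are used, some regimens begun just after assignment will be misclassified; calendar period avoids this.

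This change does not settle how controls enrolled when plasma stock runs out should be handled. That needs its own decision.
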